3. Fat Mass & Glucose Tolerance: Previous work in our laboratory demonstrated a strong relationship ($r=0.67$, $p<0.001$) between body composition and glucose area under the curve following OGTT in SCI subjects at all levels of injury. Glucose AUC was more strongly correlated ($r=0.86$, $p<0.001$) with %BF in those persons with T6-L2 SC. Additional work in our laboratory (Figure 1) has demonstrated significant relationships between visceral adipose tissue (VAT) and plasma glucose levels.[92, 93] Although relationships were also demonstrated for subcutaneous abdominal adipose tissue (SAT) and plasma glucose, these were not significant. Plasma insulin was somewhat variable presumably due to the nature and longevity of the person's glucose intolerance; those with acute glucose impairments were more likely to have hyperinsulinemia. For Individuals with SCI, increases in VAT, SAT, or VAT/SAT ratio are associated with an adverse metabolic profile, manifested by impaired glucose tolerance, insulin resistance, and dyslipidemia. [92, 93]

4. OGTT & Level of SCI. In 20 non-diabetic SCI subjects tested before exercise intervention, mean % Body Fat determined by 4-compartment modeling was 35.9 ± 6.7 ,

whereas %BF for able-bodied (AB) adults generally ranges from 12-25%. Further, Glucose AUC during 3-hour OGTT was significantly elevated in C7- T5 (965 ± 102 mg%•min) and T6-L2 SCI (723 ± 52) compared to non-diabetic AB adults (679 ± 18), and significantly different from each other ($P<0.05$); see figure 2. Of note, the glucose:insulin AUC ratio, a gross measure of insulin sensitivity, appeared elevated in our SCI subjects compared to AB adults (3.68 ± 3.02 vs 1.41 ± 0.89), although not significantly so.

5. Intravenous Glucose Tolerance Test (IVGTT). [name] learned the IVGTT procedure during his VHA and NIH Career Development Awards and has been proficient performing IVGTTs for over 18 years. [name] has supervised over 150 IVGTTs in the past 4 years, and the U Miami CTSI CRC staff routinely performs IVGTTs for several of the metabolic protocols being done there. Based on our recent results from FESLCE on glucose kinetics, HBFES LCE + Diet is expected to reduce % Body Fat and improve insulin sensitivity and glucose effectiveness during intravenous glucose tolerance tests.

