Sample size estimates were determined for the primary variables most important to the investigation, notably % Body Fat and the Insulin Sensitivity Index (SI) determined using Bergman's Minimal Model to interpret IVGTT data. For the purpose of statistical analyses, we will assume a dropout rate of 15%, although we are optimistic that persons participating in the project will actually demonstrate a better compliance rate than usual, due to the Home-Based interventions. Sample size consideration for % Body Fat (%BF) as determined by DXA was based upon body composition changes noted by Bauman et al (1994) in response to a 12-week FES leg ergometry training. % BF (Mean \pm SE) decreased from 31.8 \pm 2.3 to 28.5 \pm 2.4 for the 12 subjects monitored. Assuming a similar

change in the %BF for our HBFES LCE + Diet group and a minimal change in %BF of -0.06 for our Diet alone group, with an $\alpha = 0.05$ significance level using a Mixed Linear Model (MLM) to fit a Repeated Measures ANOVA (RMANOVA) with one between subjects factor (Group), one within subjects factor (Time) and the interaction between Group and Time and assuming both a correlation of 0.70 between the Pre and Post measurements and a correlation of 0.50 between the Pre and Post measurements. In addition, simulations were performed with the variance seen in the pilot data as well as with this variance doubled; these results are presented in Table 3. In all scenarios considered a sample size of 20 subjects per group would provide over 80% power to detect a significant Group by Time interaction. Even if 5 subjects dropped out we would still have over 80% power to detect a significant Group by Time interaction in all but one scenario.

Power Calculation for BF%				
$\alpha = 0.05$	Var(Pre)=Var(Post)=6.250	Var(Pre)=Var(Post)=12.500		
Sample Size	Empirical Power $\rho=0.70$	Empirical Power $\rho=0.50$	Empirical Power $\rho=0.70$	Empirical Power $\rho=0.50$
n=10 per group	95%	80%	76%	53%
n=15 per group	99%	95%	86%	67%
n=20 per group	100%	97%	95%	80%

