Forty subjects will be randomly assigned to either HBFES LCE + Diet or Diet alone. All tests will be two-sided at the $\alpha = .05$ level of significance. Effects will be reported with a point estimate and 95% confidence intervals in addition to p-values. We will examine the distributions of all measures and identify possible outliers. Dependent variables that are found to be non-normally distributed will be transformed to more closely approximate normality before analysis. Outliers will be thoroughly checked for collection or data entry errors before being used in the analysis. A linear regression model will be used to fit a model to assess the effects of exercise training (independent variable) on the change scores (post-score minus pre-score) for body composition, insulin sensitivity, glucose effectiveness, serum lipids and lower extremity bone mineral density (dependent variables). The linear regression model will have one between subjects (independent) factor, Group (HBFES LCE + Diet or Diet alone). While this model is exactly the same as a two-sample t-test for the change scores it allows for the adjustment of other explanatory variables that might have an impact on the dependent variable (i.e. age, time since injury, etc.). While we anticipate that randomization will balance out the groups with respect to covariates that may have an impact on dependent variables, if this is not the case the linear regression model for the change scores will allow for the inclusion of these covariates to adjust for the Group predictor variable, which are the real variables of interest in the study. Specific variables for body composition will include per cent and absolute BF, as well as per cent and absolute FFM mass, as determined by 4-compartment modeling. Insulin sensitivity (SI), glucose effectiveness (SG) will be the primary variables assessed from the IVGTT, and BMR will be assessed as a primary variable. Specific variables for serum lipids will include total cholesterol, HDL-C, LDL-c, triglycerides; hsCRP will be measured separately. Areal density (BMD) and bone mineral content (BMC) will also be considered secondary variables of interest.

Power calculations for Insulin Sensitivity (Si)				
Mean Diff(T2-T1) Group 1=0.0, Group 2=3.2				
$\alpha = 0.05$	Var(Time1)=Var(Time 2)=3.00	Var(Time1)=Var(Time 2)=6.00		
Sample Size	Empirical Power $\rho=0.70$	Empirical Power $\rho=0.50$	Empirical Power $\rho=0.70$	Empirical Power $\rho=0.50$

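### The %BF power table uses a variance about one tenth of what the quoted pilot standard errors imply; at 20 per group, power on the plan's own pilot and correlations is about 23–35%, not 80–100%.

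*Combined protocol and SAP*

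**What the plan says.** Section 10) Data Management, under Sample size determination, names %BF and insulin sensitivity as the variables on which the sample size rests. For %BF it relies on a published 12-week FES cycling study: "BF (Mean \pm SE) decreased from 31.8 \pm 2.3 to 28.5 \pm 2.4 for the 12 subjects monitored". The exercise-plus-diet group is assumed to change by a similar amount, with "a minimal change in %BF of -0.06 for our Diet alone group". Pre-post correlations of 0.70 and 0.50 are considered.

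On the spread, the section states that "simulations were performed with the variance seen in the pilot data as well as with this variance doubled". The table headings give these as "Var(Pre)=Var(Post)=6.250" and "Var(Pre)=Var(Post)=12.500". The conclusion drawn is: "In all scenarios considered a sample size of 20 subjects per group would provide over 80% power". The section adds that the loss of five subjects would leave power above 80% in all but one scenario.

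The Statistical methods text says: "All tests will be two-sided at the $\alpha = .05$ level of significance". It also says the change-score regression is equivalent to a two-sample t-test.

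Section 3.2 Previous Data, item 4, gives one other figure for %BF spread, from 20 non-diabetic SCI subjects: "mean % Body Fat determined by 4-compartment modeling was 35.9 ± 6.7".

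**The concern.** The pilot figures are labelled as mean and standard error. A standard error of 2.3 or 2.4 from 12 subjects is not a between-subject SD and has to be multiplied by √12 first. The table's base variance of 6.25 is an SD of 2.5, almost the same size as the standard errors. The case meant as a stress test, 12.5, is an SD of only 3.54, less than half of what the pilot implies.

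%BF is a primary endpoint and one of only two variables used to justify 40 subjects. If the variance is wrong by this much, the trial is likely to miss the effect it assumes. A reader who trusts the stated power could then take a non-significant %BF result as evidence that FES cycling adds nothing to diet.

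**Working it through.** **Inputs.** From section 10): pilot change 31.8 − 28.5 = 3.30; Diet-alone change 0.06 in the same direction; standard errors 2.3 and 2.4 with n = 12; correlations (ρ) 0.70 and 0.50; two-sided α = 0.05; 20 per group. Difference in change: δ = 3.30 − 0.06 = 3.24.

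**Method.** With two time points, the Group by Time test is the two-sample t-test on change scores.

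- SD of change = √(2 × Var × (1 − ρ))
- Noncentrality = δ / (SD of change × √(2/n)), with 2n − 2 degrees of freedom

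**Step 1: reproduce the plan's row (20 per group).**

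| Variance | ρ | SD of change | Power, computed | Power, stated |
|---|---|---|---|---|
| 6.25 | 0.70 | 1.94 | 99.9% | 100% |
| 6.25 | 0.50 | 2.50 | 97.9% | 97% |
| 12.5 | 0.70 | 2.74 | 95.4% | 95% |
| 12.5 | 0.50 | 3.54 | 80.6% | 80% |

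All four agree within 2 points. Of the eight cells at 10 and 15 per group, five agree within 2 points and three differ by 2.1 to 5.4 points. So 6.25, 12.5 and 3.24 are the values that were used.

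**Step 2: variance implied by the pilot.**

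- Before: SD = 2.3 × √12 = 7.97, variance 12 × 5.29 = 63.5
- After: SD = 2.4 × √12 = 8.31, variance 12 × 5.76 = 69.1
- Mean variance 66.3. Ratios: 66.3 / 6.25 = 10.6 and 66.3 / 12.5 = 5.3

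**Step 3: power with that variance.** At ρ = 0.70, SD of change = √(2 × 66.3 × 0.30) = 6.31 and noncentrality = 3.24 / (6.31 × √0.1) = 1.62. At ρ = 0.50, SD of change = √(2 × 66.3 × 0.50) = 8.14 and noncentrality = 1.26.

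| Variance | n per group | Power, ρ 0.70 | Power, ρ 0.50 |
|---|---|---|---|
| 66.3 (pilot) | 20 | 35% | 23% |
| 66.3 (pilot) | 17 (15% dropout) | 31% | 20% |
| 66.3 (pilot) | 15 | 27% | 18% |
| 132.6 (pilot doubled) | 20 | 20% | 14% |
| 44.9 (SD 6.7, section 3.2) | 20 | 49% | 32% |

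A simulation with 20,000 runs per cell gave 35% and 23% for the first row. Like for like, 35% and 23% replace the stated 100% and 97%, and 20% and 14% replace the stated 95% and 80%.

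**Step 4: what 80% power would need.** At 20 per group the standardised difference must be 0.909.

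- Detectable difference, variance 66.3: 0.909 × 6.31 = 5.7 points (ρ 0.70) to 0.909 × 8.14 = 7.4 points (ρ 0.50)
- Detectable difference, SD 6.7: 0.909 × 5.19 = 4.7 to 0.909 × 6.70 = 6.1 points
- To detect 3.24, the SD of change must be at most 3.24 / 0.909 = 3.56. That requires ρ = 1 − 3.56² / (2 × 66.3) ≈ 0.90, or 1 − 3.56² / (2 × 44.9) ≈ 0.86 with SD 6.7
- At variance 66.3 and the plan's correlations, about 60 (ρ 0.70) or 100 (ρ 0.50) per group would be needed (normal approximation)

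**The case against.** The strongest reply is that power depends on the SD of change, which the documents do not report for %BF. Repeated %BF measurements may correlate more closely than 0.70. At variance 66.3, power is 49% at a correlation of 0.80, 78% at 0.90 and 87% at 0.92. This stands as a reason to ask for the SD of change. It does not support the table, because the plan assumes only 0.50 and 0.70.

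The route to 6.25 is also an inference. The squares of 2.3 and 2.4 are 5.29 and 5.76, so 6.25 looks like a rounded-up standard error squared, but the section does not say. The pilot data could be a different dataset, or the label could be a mistake for SD. In either case, no spread given in the documents supports 6.25 as that text stands, and the text would still need correcting.

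Excluding people below 22% body fat narrows the population. If %BF is taken as normal with mean 31.8 and SD 8.14, truncation at 22 gives an SD of about 6.8. The results for SD 6.7 (49% and 32%) may then be nearer the truth, and they are still far below 80%.

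The 6.7 itself is supporting evidence only: its ± is unlabelled, and it comes from 4-compartment modelling, whereas the power section uses DXA. If it were a standard error, the spread would be larger still.

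Finally, the plan requires 95% confidence intervals, which would show the imprecision, and the enrolment dates it gives precede this version. Both limit the practical harm, but the power statement remains incorrect.

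**Conclusion.** The concern holds. The variance described as the pilot's is about one tenth of what the quoted standard errors and sample size imply, and the doubled case is about one fifth. On the plan's own difference, α, group size and correlations, %BF power is about 23–35% with the pilot variance and 14–20% with it doubled. With an SD of 6.7 it is 32–49%. No reading at the plan's correlations comes near 80%, so the claim for all scenarios and the claim after dropout both fail.

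This rests on the pilot spread being a standard error, as labelled, and on correlations of 0.50 to 0.70. A documented correlation of about 0.86 to 0.90 or higher would change the conclusion. That the standard error was taken for an SD is the likely explanation, but the numerical mismatch does not depend on it.

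**What to change.** Convert the pilot standard errors to SDs and rerun the %BF table with variances of about 45 to 66 at correlations of 0.50 and 0.70. Replace the two sentences claiming over 80% power with the resulting power and the difference detectable with 80% power at 20 per group. If a higher pre-post correlation is defensible, state it with its source and the implied SD of change. If 6.25 came from other data, or if the standard error label is wrong, say so and show the derivation.

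Keep the sample size at 40. The cost is one rerun, one table and two sentences, and a less favourable stated power. No additional subjects and no change to the analysis are needed.

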The sample size consideration for IVGTT was based on group comparisons of changes in mean response levels of insulin sensitivity to exercise between the spinal cord injury group and the able-bodied group noted within our institution in response to an exercise regime in 13 subjects with spinal cord injury. Differential equations are employed to describe glucose kinetics (assuming a single compartment model for glucose distribution) and insulin effects (assuming a separate compartment, remote from plasma) using insulin and glucose concentrations determined during the IVGTT. The resulting information provides a good estimate of glucose effectiveness, i.e., the effect of glucose at basal insulin to enhance glucose disposal, and insulin sensitivity, i.e., whole body responsiveness to an insulin challenge.[145] In these 13 subjects insulin sensitivity increased 8.24 $\mu\text{U}/\text{ml}$ with a calculated standard deviation of change of 19.74 $\mu\text{U}/\text{ml}$. A large part of both the mean change and the variability in the 13 observed patients was attributable to two extreme responders. To be conservative we assumed both a “large” change in insulin sensitivity of 3.2 $\mu\text{U}/\text{ml}$ and a “small” change of 1.6 $\mu\text{U}/\text{ml}$ and a “large” standard deviation of 6 $\mu\text{U}/\text{ml}$ and a small standard deviation of 3 $\mu\text{U}/\text{ml}$. Using a linear regression model to predict the change scores (post-score minus pre-score) with one between subjects factor (Group) and assuming both a correlation of 0.70 between the Pre and Post measurements and a correlation of 0.50 between the Pre and Post measurements and assuming both a correlation of 0.70 between the Pre and Post

measurements and a correlation of 0.50 between the Pre and Post measurements. The results of the power calculations based on the simulation is shown in table 4 (next page). In all but the most extreme scenarios considered (small mean change, large variance or low correlation) a sample size of 20 subjects per group would provide over 80% power to detect a significant Group by Time interaction. Even if 5 subjects dropped out we would still have over 80% power to detect a significant Group by Time interaction in all but the three extreme scenarios noted.

Statistical methods

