n=10 per group	99%	98%	95%	79%

n=15 per group	100%	100%	99%	90%
n=20 per group	100%	100%	100%	97%
Mean Diff(T2-T1) Group 1=0.0, Group 2=1.6				
$\alpha = 0.05$	Var(Time1)=Var(Time 2)=3.00		Var(Time1)=Var(Time 2)=6.00	
Sample Size	Empirical Power $\rho=0.70$	Empirical Power $\rho=0.50$	Empirical Power $\rho=0.70$	Empirical Power $\rho=0.50$
n=10 per group	72%	49%	45%	31%
n=15 per group	88%	68%	57%	40%

All primary and secondary outcomes will be visually assessed (boxplots, histograms, etc.) for normality and/or continuous data will be examined with a Shapiro-Wilk test. We will use a 2-way (group x time) mixed-model analysis of variance (ANOVA) to assess group interaction. Where significant interaction effects are observed, paired and independent t-tests will be used to determine significant differences within and between groups. Alpha will be set at < 5%.

11) Provisions to Monitor the Data to Ensure the Safety of Subjects

Please refer to the attached document DSMB 0719

12) Withdrawal of Subjects

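### Insulin sensitivity power: the text gives 3 and 6 as standard deviations, the table uses them as variances; with the written SDs, three of five scenarios claimed above 80% have 38–56%

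*Combined protocol and SAP*

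**What the plan says.** The SI calculation is in section 10, Data Management, under Sample size determination. It reports a pilot group of 13 subjects with a mean increase of 8.24 µU/ml and a "calculated standard deviation of change of 19.74" µU/ml, and attributes much of both to two subjects with extreme responses. It then sets its own planning values: a change of 3.2 or 1.6 µU/ml, and a standard deviation of 6 µU/ml "and a small standard deviation of 3" µU/ml. Pre-post correlations are 0.70 and 0.50.

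The table of results, printed under Statistical methods in the same section, heads its columns "Var(Time1)=Var(Time 2)=3.00" and "Var(Time1)=Var(Time 2)=6.00".

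Two power statements follow from the table. The first begins "In all but the most extreme scenarios considered (small mean change, large variance or low correlation) a sample size of 20 subjects" per group and claims more than 80% power. The second says that, with 5 dropouts, power still exceeds 80% "in all but the three extreme scenarios noted". There are eight scenarios (two differences, two spreads, two correlations), so five are claimed to exceed 80%.

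**The concern.** A variance of 3 is an SD of 1.73, and a variance of 6 is an SD of 2.45. A reader of the text believes that power was tested against SDs of 3 and 6; a reader of the table sees something much less demanding. On the variance scale the gap is a factor of 3 (9 against 3) for the small spread and 6 (36 against 6) for the large one.

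The plan names % body fat and SI as the variables that determined the sample size, and SI is a primary endpoint. If the SI result is null, its interpretation depends on whether planned power in the difference-3.2, large-spread, low-correlation scenario was 97%, as printed, or 38%.

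**Working it through.** **Inputs.** "All tests will be two-sided at the" 0.05 level (Statistical methods). The same section equates the model to a two-sample t-test on change scores. Allocation is 1:1. Differences in mean change are 3.2 and 1.6, with ρ = 0.70 or 0.50. Sample sizes per group are 20 (planned), 17 (after the assumed 15% dropout: 20 × 0.85) and 15 (the table row with 5 fewer per group).

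**Formulas.** With equal variance V at both times, SD of change = √(2V(1−ρ)). Power comes from the noncentral t distribution with 2n−2 degrees of freedom and noncentrality δ = d / (SD of change × √(2/n)), counting both tails.

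**Step 1: reproduce the printed table with V = 3 and 6.** The SDs of change are √1.8 = 1.34, √3 = 1.73, √3.6 = 1.90 and √6 = 2.45.

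- Difference 3.2, n = 10: 99.9 / 97.4 / 94.6 / 78.9% (printed 99 / 98 / 95 / 79).
- Difference 3.2, n = 20: 100.0 / 100.0 / 99.9 / 98.1% (printed 100 / 100 / 100 / 97).
- Difference 1.6, n = 15: 88.3 / 68.5 / 60.6 / 40.8% (printed 88 / 68 / 57 / 40).

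Of the 20 printed cells, 17 agree within 2 points. The other three differ by 2.8 to 3.6 points (90 against 93.2, 57 against 60.6, 31 against 28.2). The plan does not state its number of simulation replicates, but these gaps are small beside those under the SD reading, where the same cells would be 29.2, 14.9 and 8.7%.

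**Step 2: try the other readings.** As SDs at each time point (V = 9 and 36), the first row above would be 82.9 / 61.7 / 30.8 / 20.4%, and 1 of 20 cells reproduces. As SDs of the change score, none does. The table was therefore run with 3 and 6 as variances.

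**Step 3: power if the written SDs are meant.** The SDs of change become √5.4 = 2.32, √9 = 3.00, √21.6 = 4.65 and √36 = 6.00. For example, with difference 3.2, SD 6, ρ = 0.50 and n = 20, δ = 3.2 / (6 × 0.3162) = 1.69 and power is 37.6%.

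| Difference | Planning value | ρ | n=20, as variance | n=20, as SD | n=17, as SD | n=15, as SD | n per group for 80%, as SD |
|---|---|---|---|---|---|---|---|
| 3.2 | 3 | 0.70 | 100.0 | 98.9 | 97.3 | 95.3 | 10 |
| 3.2 | 3 | 0.50 | 100.0 | 90.8 | 85.4 | 80.5 | 15 |
| 3.2 | 6 | 0.70 | 99.9 | 56.4 | 49.5 | 44.5 | 35 |
| 3.2 | 6 | 0.50 | 98.1 | 37.6 | 32.6 | 29.2 | 57 |
| 1.6 | 3 | 0.70 | 95.7 | 56.4 | 49.5 | 44.5 | 35 |
| 1.6 | 3 | 0.50 | 81.2 | 37.6 | 32.6 | 29.2 | 57 |
| 1.6 | 6 | 0.70 | 73.9 | 18.6 | 16.4 | 14.9 | 134 |
| 1.6 | 6 | 0.50 | 52.1 | 13.0 | 11.7 | 10.9 | 222 |

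The first five rows are the scenarios claimed above 80%; three of them fail at n = 20. At n = 15, six of the eight are below 80%, not three.

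**Step 4: sensitivity.** If 3 and 6 were SDs of change, ρ drops out. Power at n = 20 is then 90.8% and 37.6% for 3.2, and 37.6% and 13.0% for 1.6, so the same three scenarios fail. A baseline-adjusted analysis with residual SD = SD × √(1−ρ²), which is not the planned model, would give 63.4, 47.5 and 63.4% for those three.

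**The case against.** The strongest reply is that the slip is more likely in the text than in the table. The table carries the variance label in both panels and reproduces as variances. The first power sentence itself speaks of large variance. The % body fat calculation in the same section also works in variances: "simulations were performed with the variance seen in the pilot data as well as with this variance doubled" (6.25 and 12.5), and 3 and 6 form the same kind of doubled pair. Against this stand only the words of the text and the unit µU/ml, which suits an SD rather than a variance but is also attached to the mean changes. On the variance reading the power statements stand. This is fair, and it is why the low powers are conditional. It does not remove the contradiction, because the stated powers still do not follow from the stated SDs.

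A second objection is that the count of five is partly inferred. The n = 20 row for difference 1.6 is not in the text available for this review, possibly lost in conversion from PDF. The word three comes from the dropout sentence and matches the three cells below 80% at n = 15 (68, 57 and 40%). Under the variance reading, six scenarios exceed 80% at n = 20 (the sixth at 81.2%). This is correct, but the dropout sentence refers back to the n = 20 exceptions, and two of the three failing scenarios have printed n = 20 powers of 100% and 97%. The third rests on the sentences and the printed 88% at n = 15.

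Third, the practical consequence is limited: the stated enrolment window ran to December 2024, and % body fat separately supports 20 per group in the plan. That argues against changing N, not against correcting the figures.

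**Conclusion.** The concern holds. Text and table contradict each other, and the table was run with variances of 3 and 6. If the written SDs at each time point are meant, three of the five scenarios claimed above 80% have 56.4, 37.6 and 56.4% power at 20 per group, and both power sentences are wrong. If variances are meant, the sentences stand and only the wording of the text is in error. The documents do not decide between the two.

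The figures assume the planned two-sided comparison of change scores at 0.05, equal variances at the two times and the plan's own correlations. On the variance reading, the SDs of change actually tested are 1.34 to 2.45, which is 8 to 15 times below the pilot value (19.74 / 2.45 = 8.1; 19.74 / 1.34 = 14.7). The plan discloses the pilot figure and the extreme responses behind it, so this is context for the reader rather than part of the error.

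**What to change.** State whether 3 and 6 are SDs or variances, and make the sample size text and the table agree.

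- If SDs at each time point: rerun the table with variances 9 and 36, and restate the two power sentences. If SDs of change are meant, rerun with SDs of change of 3 and 6 and say so.
- If variances: correct the wording and units in the text. A sentence on why SDs of change of 1.34 to 2.45 are reasonable beside the pilot 19.74 would help the reader, but is optional.

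Keep N = 40 in either case. The cost is at most one simulation rerun, one table and two sentences, with no extra subjects and no change to conduct or analysis. The only downside is that the stated power for SI may become less favourable.

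### The change-score model omits the outcome's baseline value and leaves its covariates open until imbalance is seen; a pre-stated baseline term is a cheap gain, but its size depends on uncertain planning inputs

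*Combined protocol and SAP*

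**What the plan says.** Section 10, Statistical methods, regresses the change score on arm: "The linear regression model will have one between subjects (independent) factor, Group (HBFES LCE + Diet or Diet alone". The text itself equates this with a two-sample t-test on change. It adds that regression can take up other variables that "might have an impact on the dependent variable (i.e. age, time since injury, etc", and gives the condition for doing so. Randomisation is expected to balance the arms, but "if this is not the case the linear regression model for the change scores will allow for the inclusion of these covariates". There is no criterion for imbalance and no closed list, and the baseline value of the outcome is not mentioned.

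The end of the same section describes another analysis: "We will use a 2-way (group x time) mixed-model analysis of variance (ANOVA) to assess group interaction". It continues: "Where significant interaction effects are observed, paired and independent t-tests will be used to determine significant differences within and between groups". Neither analysis is labelled primary.

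The sample size text works with two pre-post correlations, "assuming both a correlation of 0.70 between the Pre and Post measurements and a correlation of 0.50", and says "we will assume a dropout rate of 15" percent, which leaves 40 × 0.85 = 34 completers, or 17 per arm.

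The baseline values needed are already collected: section 7 (Overview and End of Study Assessment) has outcomes measured before and after the intervention. For DXA, the Body Composition item lists scans at screening, baseline, midpoint and end.

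**The concern.** When an outcome is measured before and after treatment, a model with arm and the baseline value estimates the arm effect at least as precisely as a change-score comparison, apart from the small cost of estimating one slope. In a 40-subject trial whose weakest body fat scenario sits at 80% power before dropout, precision available from data already in hand deserves attention.

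The covariate rule is the second part. A covariate that enters only after imbalance is seen, with no threshold and no closed list, leaves the final model to be settled after the data are visible. A term named in advance avoids that choice.

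A smaller point is that Objectives 1 and 2 ask about each arm separately, while the paired t-tests are run only after a significant interaction.

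**Working it through.** **1. Inputs.** From Sample size determination: body fat change of 31.8 − 28.5 = 3.3 points with exercise plus diet and 0.06 with diet alone, a difference of 3.24; equal pre and post variances of 6.25 or 12.5; correlation ρ of 0.70 or 0.50. From Statistical methods: two-sided 5% tests.

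**2. Reproducing the plan's power.** The variance of change is 2·Var·(1−ρ), tested with a noncentral t on 2n−2 degrees of freedom.

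| Per arm | Var 6.25, ρ 0.70 | Var 6.25, ρ 0.50 | Var 12.5, ρ 0.70 | Var 12.5, ρ 0.50 |
|---|---|---|---|---|
| 20, plan | 100% | 97% | 95% | 80% |
| 20, recomputed | 99.9% | 97.9% | 95.4% | 80.6% |
| 15, plan | 99% | 95% | 86% | 67% |
| 15, recomputed | 99.3% | 92.9% | 87.8% | 67.8% |

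The plan's figures are simulated, with the number of replicates not given. The agreement is close enough to use this as the reference analysis.

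**3. Gain from the baseline term.** With equal variances the residual variance becomes Var·(1−ρ²). The ratio of change-score to adjusted variance is 2(1−ρ)/(1−ρ²) = 2/(1+ρ). Estimating the slope multiplies this by (N−4)/(N−3).

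- N=40, ρ 0.50: 1.333 × 36/37 = 1.297, or 30% more subjects.
- N=40, ρ 0.70: 1.176 × 36/37 = 1.145, or 14%.
- N=34: the factor is 30/31, giving 1.290 (29%) and 1.138 (14%).

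Simulated ratios at N=40 were 1.290 and 1.145.

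**4. Power in the weakest body fat scenario (Var 12.5, ρ 0.50).**

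| Per arm | Change score | With baseline |
|---|---|---|
| 20 | 80.6% | 89.5% |
| 17 | 73.6% | 83.6% |
| 15 | 67.8% | 78.3% |

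The expected 95% interval half-width at 17 per arm falls from 2.47 to 2.18 points. The other three scenarios already have about 88% power or more at 15 per arm, so they gain little.

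**5. How far this depends on the inputs.** Sample size determination quotes the cited training study as mean ± SE, 2.3 before and 2.4 after, in 12 subjects. The implied variances are 12 × 2.3² = 63.5 and 12 × 2.4² = 69.1, against 6.25 and 12.5 in the power table.

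- *If the planned change-score variances are right.* They run from 2 × 12.5 × 0.5 = 12.5 down to 2 × 6.25 × 0.3 = 3.75. With Var 63.5, ρ = 1 − 12.5/127 = 0.90 to 1 − 3.75/127 = 0.97. The ratio at N=40 is then 1.023 to 0.988, a gain of +2% to −1%.
- *If ρ really is 0.50 to 0.70.* With Var 63.5 and 17 per arm, power is 21% rising to 26% at ρ 0.50, and 32% rising to 35% at ρ 0.70.

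**6. Cost.** Setting the ratio to 1 gives break-even at ρ = 2 × 36/37 − 1 = 0.946 for N=40 and 0.935 for N=34. At ρ 0.97 the loss is 1.2% (N=40) or 1.8% (N=34). Each further uninformative covariate costs about 3% at N=40: the penalty (N−3)/(N−3−k) is 1.028, 1.057 and 1.088 for k = 1, 2, 3 covariates.

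**The case against.** The strongest reply is that nothing planned is wrong. A comparison of change scores between randomised arms is valid, and the regression is already open to covariates, so the baseline value could be added. The first part stands: this is not the correction of an error. The second stands only in part, because a term that might be added after imbalance is seen has not been specified.

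The second reply is that the gain rests on correlations the plan assumes and does not estimate. This stands, and step 5 limits the claim accordingly. A reader might infer that the baseline term rescues the trial's power after dropout. The documents do not support that: under the larger variances, either the gain nearly vanishes or power is low with or without the term.

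Three other stronger readings should also be resisted.

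- *That the open list inflates the false-positive rate by a known amount.* A figure worked out for the two named covariates does not bound a list without an end, and the plan ties inclusion to imbalance, not to a favourable result. No figure is offered here.
- *That the group-by-time ANOVA is simply the same test.* Its interaction test matches the change-score test only with complete data at two time points. Dropout, or use of the midpoint DXA scan, breaks the identity.
- *That changes within each arm will go unreported unless the interaction is significant.* The plan also states: "Effects will be reported with a point estimate and 95% confidence intervals in addition to p-values". Only the t-tests are conditional; whether those effects include each arm's change is merely not explicit.

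Finally, the document is stamped v18 071825, while section 5 (Study Timelines) anticipated enrolment to December 31, 2024 and 21 weeks per subject. Outcome data may therefore exist. The documents do not say whether they have been examined, and a model changed after that would itself be a data-dependent choice.

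**Conclusion.** The point holds as an improvement in precision and pre-specification; it does not make the planned comparison invalid. The 14% to 30% gain is conditional on equal pre and post variances and on ρ between 0.70 and 0.50, and the power figures also need the plan's variances. For body fat, the standard errors the plan itself cites make a gain near zero plausible. No correlation is given for endpoints other than body fat and insulin sensitivity, so nothing is claimed for them. The case for closing the covariate list and naming one model does not depend on ρ. The change is worth making because its cost is small even where its benefit is small.

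**What to change.** Before any between-arm outcome data are examined:

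1. Name one primary model for each endpoint measured at baseline: post-value (or change) on arm plus the baseline value of that outcome, taken from the pre-intervention baseline assessment. For body fat, say which DXA scan is the baseline, since a total-body scan is also done at screening.
2. Remove the imbalance trigger and the open-ended wording. If further covariates are wanted, name a very short list in advance, chosen because they are expected to be prognostic.
3. Keep the unadjusted change-score comparison and the group-by-time ANOVA as sensitivity analyses, and label them so.
4. As a minor clarification, state that each arm's mean change will be reported with a 95% confidence interval whether or not the interaction is significant.

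If outcome data have already been examined, report the baseline-adjusted model as a labelled post hoc sensitivity analysis and leave the planned analysis in place.

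This needs a wording change and no new measurements. The statistical price is the one degree of freedom costed in step 6, plus the stated penalty for any covariate that proves uninformative.
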